5.5 Withdrawal of subjects

Each subject should be advised in the ICF that the subject has the right to withdraw from the study at any time, for any reason, without prejudice. Subjects may also be discontinued from this study if the investigator determines that it is in the subject's best interest to do so, and may be withdrawn at the investigator discretion at any time.

The withdrawal criteria are:

•	Medical Reasons	If the subject suffers from a medical condition and/or adverse events that, in the judgment of the Investigator makes it medically necessary to withdraw the subject. The specific rationale for Investigator-initiated withdrawal of a subject for medical reasons should document the specific condition for withdrawing the subject.
•	Withdrawal by Subject:	Includes consent withdrawal, subject relocation, schedule conflicts. A subject can withdraw their consent to participate in the study at their own request or be withdrawn from participation in the study at the request of their legally authorized representative at any time for any reason.
•	Lost to follow-up:	If a subject does not return for a scheduled visit, reasonable effort shall be made to contact that subject, confirm with three documented phone calls and a certified letter (delivery receipt requested) without answer before declaring the subject lost to follow-up.
•	Other:	This category is to be used for a subject who discontinues due to a reason other than as specified in the pre-defined categories above. Explain the reason for discontinuation.

The reason and date for withdrawal should be documented in the subject's source document sand eCRFs. When possible, an explanatory comment should be added to further explain the reason for the withdrawal. If withdrawal of a subject occurs during a regular study visit, the eCRF for that specific visit shall be completed as far as possible.

If withdrawal of a subject occurs between regular study visits, the subject should when possible (irrespective of the reason for withdrawal) be scheduled for a termination visit to document subject

outcome for the secondary endpoints.

If a subject is withdrawn from the study, all data collected until the time of withdrawal will be used in the analyses. Subjects who receive product and are withdrawn or discontinued from the study will not be replaced. For AEs still ongoing at the time of withdrawal, see section 8.6.11.

6 Study Products

The term "study product" refers to Sculptra Aesthetic. The study product will be provided by sponsor.

6.1 Investigational product

Sculptra Aesthetic is a poly-L-lactic acid implant in the form of a sterile non-pyrogenic suspension, which is reconstituted from a sterile dry powder by the addition of sterile water for injection. The suspension contains microparticles of poly-L-lactic acid. Poly-L-lactic acid is a biocompatible, biodegradable, synthetic polymer from the alpha-hydroxy-acid family.

Sculptra Aesthetic is available in a glass vial and is to be reconstituted prior to use by the addition of 8 mL SWFI to form a sterile non-pyrogenic suspension. 1 mL of 2% Lidocaine Hydrochloride (HCl) is to be added immediately prior to injection.

Each vial of Sculptra Aesthetic contains:

- Poly-L-lactic acid 150 mg
- Sodium carboxymethylcellulose 90 mg
- Non-pyrogenic mannitol 127.5 mg

Investigational Study Product			
Trade Name or Equivalent	Sculptra Aesthetic		
Treatment Substance Poly-L-lactic acid (PLLA)			
Concentration	367.5 mg		
Packaging	Single use vial		
Storage Conditions	 Store at room temperature, up to 30°C (86°F). DO NOT FREEZE. Refrigeration is not required. Upon reconstitution, Sculptra Aesthetic can be stored for up to 72 hours at temperatures between 5- 30°C. 		
Reconstitution Volume	8 mL SWFI		
Additional Anesthetic	1 mL of Lidocaine Hydrochloride 2% added to vial immediately prior to injection		

SALDERMA

Recommended Maximum Volume per treatment session	 Maximum of 18 mL (2 vials) of Sculptra Aesthetic will be administered per treatment session Maximum of 9 mL (1 vial) per cheek, evenly distributed within the treatment area. 		
Frequency intervals	Four (4) injection sessions with 1-month (+5 weeks).		
Reconstitution needle size	18G		
Injection needle size	25G		
Mixing Instructions	Immediate use after mix		
Injection Technique	Bolus, fanning, cross-hatching, linear threading injection technique or other techniques at the discretion of the Treating Investigator		
Injection Depth	Subdermal regions		
Treatment Area	Within the following borders:		
	□ Superior border - from top of tragus to top of alar crease		
	□ Medial border - from top of the alar crease, along the nasolabial fold (NLF) to the inferior border of the mandibular ramus		
	□ Inferior border - from medial border at mandibular ramus to angle of mandibular ramus		
	□ Lateral border - from angle of mandibular ramus to top of tragus		

6.2 Reference product

Not applicable.

6.3 Additional products and materials

The following will be supplied by the study sites:

- 18 G sterile needles (for reconstitution)
- 25 G sterile needles (for injection)
- 2% Lidocaine HCl. (Only the 3 Lidocaine products listed below should be used and only for the treatment group).
 - o 2% Lidocaine HCl- Hospira with 0.1% Methyl paraben
 - o 2% Lidocaine HCl- West Ward with 0.1% Methyl paraben
 - o 2% Lidocaine HCl- West Ward without preservatives
- Sterile Water for Injection (SWFI), United States Pharmacopeia (USP)

- Single use 5 mL sterile syringes
- Single use 1 mL or 3 mL sterile syringes
- Antiseptic (such as alcohol)

Topical or local anesthesia may be used at the discretion of the Treating Investigator before the treatment. If used, the anesthesia shall be supplied by the study site. Type of anesthesia, administration route, product name, and quantity used must be recorded in the eCRF.

6.4 Packaging, labelling, and storage

6.4.1 Investigational product

Sculptra Aesthetic is supplied as a sterile freeze-dried preparation for injection in a clear glass vial, which is sealed by a penetrable stopper, covered by an aluminum seal with a flip-off cap. Each carton of Sculptra Aesthetic contains one vial of poly-L-lactic acid, sodium carboxymethylcellulose, non-pyrogenic mannitol.

Each vial of Sculptra Aesthetic is packaged for single-use only.

Labelling will be performed according to United States Code of Federal Regulations (CFR) 21 CFR 812.5: Labelling of investigational devices. The carton will be labelled with lot number, expiration date, CTN number, and the following:

"CAUTION - Investigational Device. Limited by Federal Law to Investigational Use."

Sculptra Aesthetic can be stored at room temperature, up to 30°C (86°F). Upon reconstitution, Sculptra Aesthetic can be stored for up to 72 hours at temperatures between 5-30°C. DO NOT FREEZE. Refrigeration is not required.

Detailed product information is provided in the study IFU.

6.4.2 Reference product

No treatment control, i.e. reference product is not applicable.

6.4.3 Product accountability

The study product will be released to the Investigator or his/her authorized designee after study approvals have been received from the FDA and IRB and the CTA has been signed by all parties.

The Investigator must ensure that the study products are kept in a secure location, with access limited to those authorized by the Investigator.

The study products must be traceable from the manufacturer to their use in subjects until return or disposal. It is therefore important that the Investigator maintains accurate product accountability records, i.e. documentation of the physical location of all investigational products, deliveries, and return of investigational products between the Sponsor and the Investigator, and documentation of administration of product to the subject.

When the study is completed, all unused or expired investigational product at each study site shall be returned to the Sponsor representative for destruction, or be destroyed locally at the site if documented as agreed with Sponsor.

Any malfunctioning investigational products shall be reported as described in Section 8.7.3.

Products deliberately or accidentally destroyed during shipment or at a study site shall be accounted for and documented. Used vials, syringes, needles, and any unused material must be discarded immediately after the treatment session and must not be reused due to risk for contamination of the unused material and the associated risks including infections according to standard procedures at the site. Disposal of hazardous material, i.e. syringes and needles must conform to applicable laws and

Effective

regulations.

The study products must not be used outside of the study.

All study products sent to the Investigator will be accounted for and no unauthorized use is permitted.

6.5 Treatment

6.5.1 Treatment procedure

The investigational product is reserved for use by Treating Investigators who are experienced in treating cheek wrinkles.

Before treatment, the subject will be informed about the expected post-treatment events that should be recorded in the subject diary and potential risks involved with the treatment and when to contact the Investigator in case of emerging symptoms.

The investigational product is reserved for use by doctors trained in the appropriate injection technique. Injection procedures are associated with a risk of infection. Aseptic technique and standard practice to prevent cross-infections should be observed at all times including the use of disposable gloves during the injection procedure. All traces of make-up in the treatment area should be removed prior to any injection. The treatment site should be cleaned with a suitable antiseptic solution.

An ice pack can be applied on the site for a short period. Topical or local injection anesthesia may be used to further reduce pain on injection. If (topical or local) anesthetic or ice is used, the area should be cleaned after anesthetic is removed. The use of anesthetic or ice should be recorded in the source documentation and on the eCRFs.

Sculptra Aesthetic (sterile, freeze-dried, injectable poly-L-lactic acid) is available in 367.5 mg dose vials and will be reconstituted prior to use by the addition of 8 ml of SWFI at the investigational site following the reconstitution instructions in the study IFU.

Immediately prior to injection, 1 mL of 2% lidocaine shall be added to make a total volume of 9 mL and the vial should be shaken

For intravascular complications or embolic events, the treating physician should provide prompt medical attention and follow relevant clinical practice guidelines (8) for handling these symptoms. The treating physician should also review the Intravascular Treatment Protocol provided separately as a supportive tool.

Sculptra Aesthetic will be administered using a 25G needle. Injections will be made subdermally, i.e. in the subcutaneous and supraperiosteal region. A maximum of 18 mL (2 vials) of Sculptra Aesthetic will be administered per treatment session with a maximum of 9 mL (1 vial) per cheek, evenly distributed within the treatment area.

In this study, the study products will be administered in the Treatment area defined within the following anatomical borders:

 $\hfill\square$ Superior border - from top of tragus to top of alar crease

 $\hfill\square$ Medial border - from top of the alar crease, along the NLF to the inferior border of the mandibular ramus

 $\hfill\square$ Inferior border - from medial border at mandibular ramus to angle of mandibular ramus

 $\hfill\square$ Lateral border - from angle of mandibular ramus to top of tragus

Injection technique

The injection technique is important for the aesthetic effect of the treatment. It is recommended to use a standard injection technique for all subjects per site to limit variability due to technique. Before product is injected, aspiration should be done to avoid intravascular injection.

The injection technique is at the discretion of the investigator, proposed techniques are:

- Antegrade linear threading: also called push-ahead technique as some product is pushed ahead of the needle. Once the needle is in place, the product is injected ahead while inserting the needle in the tissue.
- Retrograde linear threading: the needle is threaded into the tissue at the appropriate depth, and the product in injected as a straight line on withdrawal of the needle
 - Bolus: multiple aliquot injections of the product is injected along a line or regions of the tissues
- Fanning: a number of linear threads to spread the product over a wider area
- Cross-hatching: combines multiple injections of linear threading that crisscross at right angle to provide volume in a square shape

6.5.2 Treatment regimen (dose and interval)

Eligible subjects randomized to the treatment group will receive a single regimen of Sculptra Aesthetic. A single regimen consists of up to 4 injection sessions with 1-month (+5 weeks) intervals. The first treatment will be administered on Day 1/ Baseline visit. Sufficient amount of study product, as determined by the Treating Investigator, should be injected to achieve optimal correction:

□ Optimal correction is defined as at least a one-step improvement on the

t and the best correction that can be achieved as agreed by Treating Investigator and subject.

□ Three additional treatment sessions may be performed if needed to achieve optimal correction, as determined by the Treating Investigator and subject.

Treatment will stop when optimal correction has been achieved and subsequent visits will be followup visits. Treatment will not be performed if the subject has a disease or condition described in the exclusion criteria, or an ongoing treatment-related AE that in the opinion of the Treating Investigator would be worsened by a treatment.

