4.3 Duration of subject participation

The total duration of the study is expected to be 17 months. A subject will be involved in the study for up to 13.5 months.

Note: One month is defined as 4 weeks in the study.

End of study is when enrollment has reached the target number of subjects and all subjects have completed the last study visit.

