4.7 Visits

Table 1 Schedule of events for Treatment Group

	Visit 1	Visit 2	Visit 2a	Visit 3	Visit 3a	Visit 4	Visit 4a	Visit 5	Visit 5a	Visit 6 & 7	Visit 8
	Screening ¹	Baseline/ Treatment 1 ¹	Telephone Contact	Treatment 2 ⁴ (Optional)	Telephone Contact	Treatment 3 ⁴ (Optional)	Telephone Contact	Treatment 4 ⁴ (Optional)	Telephone Contact	Follow-up	Final visit/Early termination
	(≤ 30 days of Baseline)	Day 1 Baseline	72 hours (±24 hrs) after Treatment 1	1 month (+5 weeks) after Treatment 1	72 hours(±24 hrs) after Treatment 2	1 month (+5 weeks) after Treatment 2	72 hours (±24 hrs) after Treatment 3	1 month (+5 weeks) after Treatment 3	72 hours (±24 hrs) after Treatment 4	Month 7 (+2 weeks) Month 9 (+ 2 weeks) after Baseline	Month 12 (+ 2 weeks) after Baseline
Informed consent	X	2		-		1					
Inclusion/Exclusion criteria	x	X ³		X ³		X ³		X ³		7	
Demographics incl height and weight Medical history	X X	X9 X3								X9	X9
Previous therapies	X										
Concomitant therapies	X	Х	X	Х	Х	Х	X	Х	X	Х	X
Urine pregnancy test ²	X	X ³		X ³		X3		X ³			
Randomization		X ³									
Photography (2 D and 3D)		X ³		X		Х		X		X	X
Sculptra Aesthetic administration		X		X ⁴		X4		X ⁴			
Adverse events assessment		X	X	Х	X	Х	X	X	X	Х	X
Safety assessments8	X	Х		Х		Х		X		Х	X
Visual Function assessments ¹⁰	X	X ^{3,7}		X ^{3,6,7}		X ^{3,6,7}		X ^{3,6,7}		Х	X
Device deficiencies		X		X ⁶		X ⁶		X ⁶			
Dispense subject diary	7	X	1	X ⁶		X ⁶		X ⁶			
Collect subject diary		1		X ³		X ^{3,5}		X ^{3,5}		X ⁵	
Ultrasound (at selected sites)		X3		5		6		(Х	X
				Treating In	vestigator Assessme	nts	a	52	26	40	
GAIS				X ³		X ³		X ³		x	Х
Radiance, skin tightness and jawline contour										х	х
	X ³	X ³		X ³		X ³		X ³			
				Blinded F	valuator Assessment	s		*			n
	X ³	X ³								x	х
				Sub	ject Assessments	ar			9.0	ar mar	
GAIS				X ³		X ³		X ³		Х	X
Subject satisfaction questionnaire				X ³		X ³		X ³		Х	Х
FACE-Q	7	X ³		X ³		X ³		X ³		X	X

 Screening and baseline visits may occur on the same day, if visits occur the same day assessments will not be duplicated

2. Females of childbearing potential

- 3. Pre-treatment
- 4. If treatment is not performed this is a follow-up visit

5. If applicable (i.e. if treatment was performed at the previous visit)

Abbreviations: GAIS (Global Aesthetic Improvement Scale), C

6. If applicable (i.e. if treatment is performed at this visit)

7. 30 minutes post-treatment

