- Instruct the subject to complete Face-Q assessment.
- Assess whether optimal treatment result has been obtained (as agreed by the Treating Investigator and Subject).
 - If a second treatment is to be performed, confirm eligibility criteria
 - No treatment should be given in the subject has a disease or condition described in the exclusion criteria, or an ongoing treatment related AE that in the opinion of the Treating Investigator would be worsened by a treatment.

For subjects who receive a second treatment:

- Prior to any treatment being provided, perform UPT for all females of childbearing potential. The test result must be negative for a subject to receive treatment.
- Administer Sculptra Aesthetic.
- Evaluate for device deficiencies.
- o 30 minutes following injection, perform Visual Function Assessments.
- Dispense new subject diary and instruct subject on daily diary completion. Remind subject to bring the diary to the next on-site visit.
- Evaluate the subject for post-treatment AEs- Treating Investigator.
- Schedule the next follow up visit (1 month +5 weeks) after treatment 2 visit
 - 4.7.5 Visit 3a, Follow up 72 hour telephone call (±24 hours) *for treatment group only, subjects who received a second treatment.*
- o Interview subject regarding any concomitant therapies
- Interview subject regarding any AEs that have occurred since receiving treatment. If AEs are reported, notify the Investigator immediately and determine whether subject should return to the site for an unscheduled visit. The Investigator should assess all reported AEs in a timely manner.
- Interview subject regarding the Diary completion and reported events since receiving treatment. Remind subject to complete the Diary daily and bring it to the next on-site visit.

4.7.6 Visit 4, Treatment 3 (1 month (+5 weeks) after Treatment 2) - for treatment group only

• Review the subject's concomitant therapies.

- Collect and review subject diary (only applicable for subjects who received a treatment at Treatment 2 visit).
- Interview for AEs.
- Assess for AEs- Treating Investigator
- Assess Treating Investigator (if receiving a treatment at this visit, perform prior to treatment)
- Obtain Photography 2D and 3D (if receiving a treatment at this visit, perform prior to treatment)
- Perform Visual Function Assessments for all subjects (if receiving a treatment at this visit, perform prior to treatment).

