- Perform safety assessments: Cheek sensation, Cheek firmness, symmetry and function, Mass formation and Device Palpability.
- GAIS: Perform GAIS assessment (if receiving a treatment at this visit, perform prior to treatment) Investigator and Subject.
- Instruct the subject to complete the Subject satisfaction questionnaire (pre-treatment).
- Instruct the subject to complete Face-Q assessment.
- Assess whether optimal treatment result has been obtained (as agreed by the Treating Investigator and Subject).
 - If a third treatment is to be performed, confirm eligibility criteria
 - No treatment should be given in the subject has a disease or condition described in the exclusion criteria, or an ongoing treatment related AE that in the opinion of the Treating Investigator would be worsened by a treatment.

For subjects who receive a third treatment:

- Prior to any treatment being provided, perform UPT for all females of childbearing potential. The test result must be negative for a subject to receive treatment.
- Administer Sculptra Aesthetic.
- Evaluate for device deficiencies.
- \circ 30 minutes following injection, perform Visual function Assessments.
- Dispense new subject diary and instruct subject on daily diary completion. Remind subject to bring the diary to the next on-site visit.
- \circ $\;$ Evaluate the subject for post-treatment AEs- Treating Investigator.
- \circ Schedule the next follow up visit (1 month +5 weeks) after treatment 3 visit

4.7.7 Visit 4a, Follow up 72 hour telephone call (±24 hours) - for treatment group only, subjects who received a third treatment.

- o Interview subject regarding any concomitant therapies
- Interview subject regarding any AEs that have occurred since receiving treatment. If AEs are reported, notify the Investigator immediately and determine whether subject should return to the site for an unscheduled visit. The Investigator should assess all reported AEs in a timely manner.

• Interview subject regarding the Diary completion and reported events since receiving treatment. Remind subject to complete the Diary daily and bring it to the next on-site visit.

4.7.8 Visit 5, Treatment 4 (1 month (+5 weeks) after Treatment 3) - *for treatment* *group only*

- Review the subject's concomitant therapies.
- Collect and review subject diary (only applicable for subjects who received a treatment at Treatment 3 visit).
- Interview for AEs.
- Assess for AEs- Treating Investigator

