- Interview subject regarding the Diary completion and reported events since receiving treatment. Remind subject to complete the Diary daily and bring it to the next on-site visit.

4.7.10 Visits 6, 7 and 8, Follow-up month 7 (+ 2weeks), 9 (±2 weeks), 12 (±2 weeks) all subjects

- Obtain weight measured at clinic.
- \circ Review the subject's concomitant therapies.
- Collect and review subject diary (only applicable for subjects in the treatment group who received a treatment at Treatment 4 visit).
- Obtain 2D and 3D Photographs.
- Perform ultrasound (at selected sites).
- Interview for AEs
- Perform safety assessments: Cheek sensation, Cheek firmness, symmetry and function, Mass formation and Device Palpability (treatment group only for device palpability).
- Perform Visual function assessments: Snellen visual acuity test, Extraocular muscle function test and Confrontation visual field
- Assess for AEs- Treating Investigator
- Assess GAIS Investigator and subject.

assessment - Blinded

Evaluator.

0

- Radiance, skin tightness and jawline contour: Perform radiance, skin tightness and jawline contour assessment Treating Investigator.
- Instruct the subject to complete the Subject satisfaction questionnaire (treatment group only).
- Instruct the subject to complete Face-Q assessment.

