8.2 Subject Diary Data

A subject diary will be dispensed to all subjects for daily completion for 28 days beginning on injection day for each treatment with direct questioning for pain, tenderness, redness, bruising, swelling, itching, lumps/bumps and "other".

The subject will also be specifically instructed to record presence of any of the following symptoms in the "other" section; Changes in vision (i.e. loss of vision, blurriness, double vision, pain in or around your eye, blindness, blind spots, problems moving your eyes), Skin changing color around the eyelids, Crusty or scabby skin around the eyelids, Pain, Headache, Fever, Dizziness, Confusion, Weakness or numbness in the arms or legs, Changes to consciousness or alertness, Difficulty speaking/ speech impairment or Face droop. The diary will include specific instructions to seek immediate medical attention if any of these symptoms or signs are observed.

Diary data will be counted and displayed separately from other AE data.

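### A fourth injection late in its permitted window can leave its 28-day diary unfinished at month 7, the visit where the schedule points to its collection, which shortens the symptom-day counts

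*Protocol*

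**What the plan says.** **Timing of injections.** Protocol 6.5.2 says "A single regimen consists of up to 4 injection sessions with 1-month (+5 weeks) intervals" and "The first treatment will be administered on Day 1/ Baseline visit". Section 4.3 fixes the unit: "Note: One month is defined as 4 weeks in the study". Each window is counted from the preceding treatment. Section 4.7.4 tells the site: "Schedule the next follow up visit (1 month +5 weeks) after treatment 2 visit". The heading of section 4.7.8 is "Visit 5, Treatment 4 (1 month (+5 weeks) after Treatment 3", and Table 1 agrees: "1 month (+5 weeks) after Treatment 3".

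**Timing of month 7.** Table 1 and section 4.7.8 count this visit from baseline, with a window of plus 2 weeks and nothing on the minus side. It is not tied to the last injection.

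**Diary.** Section 8.2 has it dispensed "for daily completion for 28 days beginning on injection day for each treatment". After treatment 4, section 4.7.8 has the subject reminded to bring it to the following clinic visit, which is month 7. Table 1 marks collection in the joint column for Visits 6 and 7, and footnote 5 limits this to subjects treated at the visit before. Section 4.7.10, which covers Visits 6, 7 and 8 together, lists collection as "only applicable for subjects in the treatment group who received a treatment at Treatment 4 visit".

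**Use of the data.** The second safety endpoint (Protocol 3.2, SAP 1.6) is the incidence, intensity and number of days of expected events over 28 days from each treatment. Protocol 10.5 and SAP 2.5.2 report the days in four categories: 1, 2-7, 8-14 and 15-28.

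**The concern.** The injection windows accumulate from one session to the next, while the month 7 visit stays fixed to baseline. At the late end of the windows the two come closer together than the length of a diary.

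The diaries for treatments 1 to 3 are protected. The interval has no minus side, so the next visit is at least 28 days later. The treatment 4 diary has no such protection: neither document gives a latest date for treatment 4 or a minimum gap before month 7.

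At stake is the duration part of the diary safety endpoint. A diary handed in early can only lose days with symptoms, so the error runs one way, toward shorter reactions. SAP 2.4.5 censors return to social engagement at the last diary entry, but neither document has a matching rule for shortened diaries in the symptom-day counts. Safety data are summarized on observed cases (Protocol 10.6, SAP 2.4.2).

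**Working it through.** The plan gives no figure for the latest fourth injection or for its distance from month 7, so there is nothing to reproduce. What follows is calendar arithmetic on the plan's own windows.

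**Inputs**
- Month: 4 weeks (Protocol 4.3).
- Interval between sessions: 4 weeks to 4 + 5 = 9 weeks, each counted from the previous treatment (Protocol 6.5.2, 4.7.4, 4.7.8, Table 1).
- Treatment 1: week 0 (Protocol 6.5.2).
- Month 7 visit: 7 × 4 = week 28, to 28 + 2 = week 30, from baseline (Table 1).
- Diary: 28 days from the injection (Protocol 8.2).

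**Range for treatment 4**
- Earliest: 3 × 4 = week 12 (day 84).
- Latest: 3 × 9 = week 27 (day 189).
- Total slack: 27 − 12 = 15 weeks.

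**Diary days available at month 7** = min(28, visit day − injection day), with the visit at day 196 (week 28) or day 210 (week 30):

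| Treatment 4 | Visit at week 28 | Visit at week 30 |
|---|---|---|
| Week 12 | 28 | 28 |
| Week 24 | 28 | 28 |
| Week 25 | 21 | 28 |
| Week 26 | 14 | 28 |
| Week 27 | 7 | 21 |

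**Thresholds**
- Up to week 24 the diary is always complete at month 7.
- After week 24 it may be short, depending on where in its window month 7 is booked. This needs a mean interval above 24/3 = 8 weeks, that is, more than 24 − 12 = 12 of the 15 weeks of slack.
- After week 26 it must be short if collected at month 7. This needs a mean interval above 26/3 = 8.67 weeks, that is, more than 26 − 12 = 14 of the 15 weeks.

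**Effect on the day categories.** With 7 diary days, neither 8-14 nor 15-28 can be reached. With 14 days, 15-28 cannot be reached. With 21 days the top category can be reached, but the count stops at 21.

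**Later visits.** Month 9 is 9 × 4 = 36 ± 2, or weeks 34 to 38. That is 7 to 11 weeks after an injection at week 27, so the diary would be complete. Month 12 is 12 × 4 = 48 ± 2, or weeks 46 to 50, which is 19 to 23 weeks after it.

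**The case against.** The strongest reply is that section 4.7.10 already allows later collection, because it lists the treatment 4 diary under Visits 6, 7 and 8 without confining it to month 7. This stands in part. The plan does not say outright that the diary is collected only at month 7. But footnote 5 and the reminder in section 4.7.8 both point there, and nothing tells a subject to keep an unfinished diary. The passages disagree, and a site that follows Table 1 will collect early.

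Second, the case is rare. Sessions 2 to 4 are optional, treatment stops at optimal correction, and between weeks 24 and 26 a month 7 visit booked late enough in its window still leaves 28 days. All of this stands. A reader might infer that the windows and the collection rule can never be met together; that is true only after week 26 with collection at month 7.

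Third, safety information is not lost, since adverse events are asked about at every visit, including months 7, 9 and 12. That is right for adverse events in general. It does not repair the diary counts, which section 8.2 keeps separate from other adverse event data.

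Two stronger readings are tempting:

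- **Month 7 responder rates are distorted or unblinded.** An injection can precede the blinded month 7 assessment by as little as one week, and controls receive no injections. Section 4.4.2 covers discussion and documents but not visible signs. So an effect on the grade or the blinding is plausible. No figure in the documents shows that reactions at 7 to 21 days do either. The endpoint is secondary, and Protocol 10.4 gives its p-value only as an aid to interpretation.
- **Month 6 visits pooled as month 7 (SAP 2.4.2) may precede treatment 4.** The SAP revision history attributes the move from month 6 to month 7 to version 4 of the protocol. The treatment windows under which those visits took place are not in the documents, so the current windows cannot be applied to them.

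**Conclusion.** The point holds as a minor gap between schedule and data collection. The treatment 4 diary may be incomplete at month 7 if the injection falls after week 24, and must be if it falls after week 26 and the diary is collected then. At week 27, 7 to 21 of 28 days (25% to 75%) are available. The day-count categories of the diary safety endpoint then lean toward shorter durations.

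This assumes that delays accumulate as the windows are written, that the subject has all four sessions at long intervals, and that sites follow Table 1 and section 4.7.8. The number of such subjects is not given and is probably small. The study flow chart is not shown, so a limit stated only there could not be checked.

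A reader might carry the concern over to the primary result. The documents do not support that: the primary assessment is at month 12, at least 19 weeks after the latest permitted injection.

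**What to change.** The sponsor should reconcile four items: the treatment windows, the month 7 window, Table 1 footnote 5 and section 4.7.10. Which schedule is right is for the sponsor to decide.

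Whatever is decided, one data rule is worth adding: collect the treatment 4 diary at the first on-site visit at least 28 days after that injection, month 9 if needed, and have the subject keep it until then. Section 4.7.10 already leaves room for this, so the change amounts to the footnote and the reminder in section 4.7.8. The cost is a later diary return for a few subjects.

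Optionally, the SAP could add a supportive month 7 responder summary that leaves out subjects assessed within 28 days of an injection. It costs one table and would show whether recent injections matter to that result. The primary analysis does not change.
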